9.4 Interim Analyses and Stopping Rules

No interim analyses are planned as they relate to either the primary or secondary outcome data. An individual subject would be discontinued from the study intervention if a medical condition develops that precludes the continuation of the treatment intervention. Additionally, the study will be stopped if the IMC, in consultation with NICHD, decides that the risks associated with the treatment interventions (i.e., excessive SAEs) outweigh the potential benefits of the knowledge gained from continuing the study.

9.5 Outcomes

9.5.1 Primary Outcome

The co-primary clinical outcomes are pain and disability, which will be assessed at pre-treatment baseline (visit 1) and at 1-, 6-, 12-, 24-, and 48-weeks post-treatment (i.e., visits 20-24).

9.5.2 Secondary Outcomes

Secondary outcomes include expected pain, expected harm, and lumbar flexion during standardized reaching, which will be measured at pre-treatment baseline (visit 1), at the beginning of each week during treatment (visits 2, 5, 8, 11, 13, 15, 17, 18, 19), and at 1-, 6-, 12-, 24-, and 48-weeks post-treatment (i.e., visits 20-24).

9.6 Data Analyses

We will analyze all outcome variables (pain, disability, pain/harm expectancy, and lumbar flexion) using linear mixed-effects (LME) models with treatment (Experimental, Control) as a between-subject fixed effect and time (pre-treatment, 1, 6, 12, 24, and 48 weeks) as a within-subject fixed effect. Given the expected findings, both linear and quadratic time effects will be tested in every model. We will also include demographic covariates (e.g., age, BMI) and potential confounders (e.g., radiating versus non radiating pain) as well as sex stratification in the LME models. Any variables that differ at baseline will be included in the statistical models as potential confounders.

Intention-to-treat analyses are commonly conducted to analyze randomized clinical trial data in the presence of missing values. While various imputation strategies have been proposed to estimate missing data, such as last observation carried forward, use of LME models to analyze longitudinal data renders these strategies largely unnecessary. We will also conduct equivalent per-protocol analyses that will include only successfully adhered participants (i.e., attending $\geq 70\%$ of gaming sessions).

Aim 1. Examine immediate clinical outcomes as a function of treatment. Relative to

the control group, participants in the experimental group will show greater reductions in pain and disability at post-treatment relative to pre-treatment baseline (Hypothesis 1).

To test Hypothesis 1, we will examine the Treatment by Time (baseline-post treatment) interaction in a LME model: a greater reduction in pain and disability in the experimental group than in the control group.

Aim 2. Examine potential mechanisms of pre- to post-treatment changes in clinical outcomes. Participants in the experimental group will exhibit greater pre- to post-treatment decreases in pain/harm expectancy and increases in lumbar flexion as compared to the control group (Hypothesis 2.1). Decreases in pain/harm expectancy and increases in lumbar flexion will be positively related to pre- to post-treatment reductions in pain and disability (Hypothesis 2.2).

Aim 3. Examine maintenance of treatment gains at 1-, 6-, 12-, 24-, and 48-weeks post-treatment. Relative to the control group, participants in the experimental group will continue to show lower levels of pain and disability at each time point as well as increased activity in their natural environment (Hypothesis 3).

To address aims 2 & 3 we will build and test linear mixed-effects models for each of the outcome variables. For hypotheses 2.1 and 3, pain, disability, pain/harm expectancy, and lumbar flexion will be the outcome variables, while time (linear and quadratic), treatment group, and the interactions of time and treatment group will be the primary predictor variables. For hypothesis 2.2, pain/harm expectancy and lumbar flexion will serve as the outcome variables, while time (linear and quadratic), treatment group, the time-by-group interactions, pain, and disability will be predictor variables. For hypothesis 3, planned comparisons will be conducted to compare the control and experimental groups at each time period for pain, disability, and activity levels in the natural environment. As noted above, covariates will be added to analyses as needed. The significance level for every omnibus test will be set to 0.05, while Holms procedure will be used to control familywise type-I error rate for post-tests at .05.

Checking Assumptions: Assumptions of LME models will be checked by conducting analyses of model residuals. Violations of normality will be addressed by transforming the data, while outliers or influential cases will be handled by conducting sensitivity analyses. In contrast to the standard repeated measures analyses of variance, with their rigid assumptions about the error covariance structure, LME models permit numerous alternative error covariance structures. This allows for modeling of data that exhibit both heteroscedasticity and autocorrelation, which is likely to characterize the data collected for this study.

Additional Analyses: We will use the same analytic framework to analyze additional measures of core outcome domains, including emotional functioning (e.g., CES-D, POMS-2, PROMIS measures), pain vulnerability (TSK, PCS), pain resilience (PRS, PSEQ), and patient global impression of change (PGIC).

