6. STUDY PROCEDURES

6.1 Schedule of Evaluations

Assessment	Prescreen	Screen Visit 0	Enrollment & Baseline Visit 1	Treatment Visits 2-19	Post-Treatment Assessments Visit 20	Post-Treatment Assessments Visits 21-24
Numeric Pain Rating Scales 7-day & 24-hour	X	X	X	X*	X	X
Roland-Morris Disability Questionnaire	X	X	X		X	X
Fear Question	X	X				
Medical History - Back Pain	X	X				
Medication Log		X	X	X	X	X
Informed Consent Form		X				
Inclusion/Exclusion Criteria		X				
Enrollment/Randomization		X				
Medical History		X				
Physical Exam Form		X				
Adverse Events			X	X	X	X
Numeric Pain Rating Scale - Right Now			X	X	X	X
Standardized Reaching Paradigm • Pain & Harm Expectancy • Lumbar Spine Flexion			X	X*	X	X
Tampa Scale for Kinesiophobia			X		X	X
Center for Epidemiologic Studies - Depression			X		X	X
Pain Catastrophizing Scale			X		X	X
Pain Resilience Scale			X		X	X
Pain Self Efficacy Questionnaire			X		X	X
Brief Pain Inventory - Short Form			X		X	X
PROMIS-Anxiety			X		X	X
PROMIS-Depression			X		X	X
PROMIS-Positive Affect			X		X	X
PROMIS – Meaning and Purpose Scale			X		X	X
Life Fulfillment Scale			X		X	X
Profile of Mood States			X		X	X
Real World Activity Monitoring			X		X	X
Treatment Evaluation Inventory - Short Form			X		X	
Patient Global Impression of Change					X	X

*assessed at the first visit of each week

Note: Prescreening, Visit 0 screening, Visit 1 baseline, and Visit 2 first intervention can all occur on the same day.

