6.2.4 Follow-up Visits

Treatment visit assessments for each visit 2-19 include the following:

- Numeric Pain Rating Scales 7-day & 24-hour
- Medication Log
- Adverse Events Log
- Numeric Pain Rating Scale – Right Now
- Standardized Reaching Paradigm (Pain & Harm Expectancy, Lumbar Spine Flexion)

Assessments at first post-treatment follow-up visit, Visit 20, include:

- Numeric Pain Rating Scales 7-day & 24-hour
- Roland-Morris Disability Questionnaire
- Medication Log
- Adverse Events Log
- Numeric Pain Rating Scale – Right Now
- Standardized Reaching Paradigm (Pain & Harm Expectancy, Lumbar Spine Flexion)
- Tampa Scale for Kinesiophobia
- Center for Epidemiologic Studies – Depression
- Pain Catastrophizing Scale
- Pain Resilience Scale
- Pain Self Efficacy Questionnaire
- Brief Pain Inventory – Short Form
- PROMIS-Anxiety
- PROMIS-Depression
- PROMIS-Positive Affect
- PROMIS-Meaning and Purpose Scale
- Life Fulfillment Scale
- Profile of Mood States
- Real World Activity Monitoring
- Treatment Evaluation Inventory – Short Form
- Patient Global Impression of Change

Assessments at post-treatment follow-up visits 21-24 include:

- Numeric Pain Rating Scales 7-day & 24-hour
- Roland-Morris Disability Questionnaire
- Medication Log
- Adverse Events Log
- Numeric Pain Rating Scale – Right Now
- Standardized Reaching Paradigm (Pain & Harm Expectancy, Lumbar Spine Flexion)
- Tampa Scale for Kinesiophobia
- Center for Epidemiologic Studies – Depression
- Pain Catastrophizing Scale
- Pain Resilience Scale

- Pain Self Efficacy Questionnaire
- Brief Pain Inventory – Short Form
- PROMIS-Anxiety
- PROMIS-Depression
- PROMIS-Positive Affect
- PROMIS-Meaning and Purpose Scale
- Life Fulfillment Scale
- Profile of Mood States
- Real World Activity Monitoring
- Treatment Evaluation Inventory – Short Form

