7. SAFETY ASSESSMENTS

Threats to Individual Privacy and Data Confidentiality: To minimize risk to participant privacy, all study procedures are conducted in private testing rooms by qualified study personnel and the collection of sensitive information is limited to the minimum necessary to conduct the necessary screening and testing. To minimize risk to participant confidentiality, we will use secure web-based applications (i.e., REDCap) to collect and manage participant information and all data will be stored with unique identification codes such that no personal identifying information will be available in the study files. All data collection forms are electronic Case Report Forms (eCRF). As source documents, all forms are signed or electronically verified and dated by a study staff member. In case of interruption of internet connectivity during data collection, participants will complete a paper version of the eCRF and the Study Coordinator or Research Assistant will transfer all data from the paper forms to the database. Every 2-weeks a Research Assistant will perform a quality assurance check by comparing data entered into the database from paper-based forms. All paper data collection forms will be kept in locked file cabinets located in locked testing rooms.

Voluntary Reaching Task: Bending of the trunk could possibly aggravate current low back pain symptoms; however, these reaching tasks have been chosen because they mimic everyday activities and are within the available range of motion of individuals with low back pain. The reaching tasks minimize potential risks to the participant in that they do not require any lifting; thus, spine loads are minimal. Risk is further minimized because we inform all participants that they are free to stop at any time if they find the procedure too uncomfortable. We have been conducting this reaching protocol with back pain participants for more than a decade and we have never had any incidents of injury or sustained aggravation of back pain symptoms.

Virtual Reality Game Play: Consistent with our Phase I trial, prior to testing participants will be fully informed of the game procedures, including information on the available rewards for performance. The movements required during video game play will be very similar to those required to perform the reaching tasks and will be within the available range of motion of individuals with low back pain. The game play

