7.1 Specification of Safety Parameters

At each visit the study staff will use the Adverse Event Log to ask the study participants if they have had any change in general health since the last visit. If fever or unexplained weight loss is reported, suggesting systemic infection / disease may be causing their low back pain, the clinician will do a basic physical exam and specifically assess for the possibility they have other systemic illness. They will be advised to seek medical care and research participation may be delayed, temporarily discontinued, or permanently suspended at the discretion of the examining clinician and in consultation with the Medical Directors if needed.

Before each treatment the study staff will use the Contraindications Form to inquire about change in back related signs indicative of increased severity of symptoms. Specifically if they have any new symptoms such as weakness, numbness, or difficulty walking. If the study participant reports yes on any of these items the clinician will do a basic physical exam and assess neurological function by checking myotomes, dermatomes, and reflexes to determine whether the study participant now presents with hard neurological signs (e.g., loss of motor function, significant changes in reflexes), or symptoms of other systemic disease. If the participant does present with hard neurological signs or serious systemic disease, they will be encouraged to seek consultation with their personal physician, and they will be excluded from further participation from the study.

All negative changes in health status other than back pain will be recorded as

Adverse Events, logged, and reported per requirements of the Virginia Commonwealth University IRB and NIH. In the case of dismissal from the protocol for the above stated reasons, the Medical Safety Committee will meet to determine whether the AE was caused by the intervention (Definite, Probable, Possible, Unknown) and an adverse event report will be filed according to the specific requirements of the Virginia Commonwealth University IRB and NIH.

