7.3 Adverse Events and Serious Adverse Events

Adverse events: A structured safety monitoring system will be established to both assure real-time participant care and unbiased monitoring of adverse events (AE). For ongoing participant safety, events will be assessed by the PIs and co-investigators to determine if they are Serious, Unexpected, and/or On-site. If so, an event evaluation form will be completed that will include a description of the event, a classification of seriousness, assessment of potential relationship to the intervention, assessment of need for change in the consent or the study activities, a summary of known prior health issues, event outcome, and a classification of the main organ system involved. (See Protection of Humans Subjects for definitions of adverse events).

Adverse Events include any reaction, side effect, or other untoward medical event, regardless of the relationship to the study intervention. For ongoing participant

safety, any adverse events will be characterized within 24 hours by the study team to determine if it was Non-series/Serious, Unexpected/Expected, and Off-site/On-site.

Non-serious adverse events will be defined as conditions that may be unpleasant and bothersome to the participant (e.g., mild nausea) that do not require discontinuing the study intervention or components of the intervention. All adverse events will be documented for review by the Independent Monitoring Committee (IMC) and reported to the IRB. Serious events includes any event that is 1) life threatening, 2) may result in prolonged, permanent, or severe disability, 3) may worsen a pre-existing condition, or 4) requires inpatient hospitalization or surgical procedure, or a treatment to prevent a serious event. All serious adverse events will require immediate notification of a Physician, 24 hour notification of the IRB, and an assessment of the implications for the continuation of the study and/or modification of the consent form.

Unexpected adverse events are defined as events that are not listed in the consent form. Monitoring for unexpected serious adverse events attributable to the intervention is the responsibility of the investigators. Specific reporting and review requirements are defined for unexpected events, so that, if an unexpected event is found to be related to the intervention, the protocol and consent can be modified.

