We will utilize the NCI Common Terminology Criteria for adverse Events which are a descriptive terminology that can be utilized for Adverse Event (AE) reporting and provides a grading (severity) scale for each AE. AEs will be labeled according to severity, which is based on their impact on the patient.

Attribution: An assessment of the relationship between the AE and the intervention will be performed using the NCI guidelines which do not define an AE as necessarily “caused by a therapeutic intervention”, after naming and grading the event, the clinical investigator will assign an attribution to the AE as unrelated, unlikely, possible, probable, or definite.

Note that back pain is not considered an adverse event within this research.

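### Back pain is not an adverse event, and pain is compared by arm only at Visit 1 and Visits 20-24, so a flare during treatment that settles before the Visit 20 recall window enters no stated by-arm result

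*Combined protocol and SAP*

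**What the plan says.** **Adverse events.** Section 7.3 states: "Note that back pain is not considered an adverse event within this research". Section 7.1 has the same exclusion in its recording rule: "All negative changes in health status other than back pain will be recorded as" adverse events.

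**Pain as an outcome.** Section 9.5.1 names pain and disability as co-primary, "which will be assessed at pre-treatment baseline (visit 1) and at 1-, 6-, 12-, 24-, and 48-weeks post-treatment (i.e., visits 20-24". The models in section 9.6 take "time (pre-treatment, 1, 6, 12, 24, and 48 weeks) as a within-subject fixed effect". Hypothesis 1 is tested from baseline to post-treatment, and the group comparisons for Hypothesis 3 belong to Aim 3, whose time points are all post-treatment.

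**Pain as collected.** The table in section 6.1 marks the 7-day and 24-hour ratings in the treatment column with the footnote "assessed at the first visit of each week". It marks the current-pain rating for Visits 2-19 without that footnote.

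**Safety.** The précis (Design and Outcomes) says the trial tests efficacy and safety. Sections 1.1 and 1.2 list no safety objective. Section 7, on the reaching task, says: "Bending of the trunk could possibly aggravate current low back pain symptoms". It then describes game movements as very similar to the reaching movements.

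**The concern.** The arms differ in how much lumbar flexion the game demands: targets set for 15 to 60 degrees with further gain adjustment in the experimental arm, against 15 degrees in the control arm (section 5.1). Aggravated back pain is the most foreseeable harm of that difference, and it is the one event that the adverse event rules leave out.

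Section 2.1 reports that three daily sessions in Phase I did not exacerbate existing back pain. This trial extends exposure to 18 sessions over nine weeks. Followed as written, it could report lower mean pain at Visit 20, and adverse events free of back pain by rule, without saying whether flares during play differed between arms. What is at stake is the completeness of the safety report.

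**Working it through.** The plan gives no figure for this point, so there is none to reproduce. The check compares sections and sums visit windows.

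**1. Is there any by-arm pain result between Visits 2 and 19?**
- Section 9.5.1: pain at Visit 1 and Visits 20-24 only.
- Section 9.6 models: six time levels, none during treatment.
- Hypothesis 2.2: pain is a predictor of expectancy and flexion, with no visits named, so the model yields no by-arm pain result.
- Additional Analyses: emotional functioning, pain vulnerability, pain resilience and global impression of change.
- Section 9.5.2 does name weekly treatment visits, but for expected pain, expected harm and lumbar flexion. The time list in 9.6 leaves those out too, so the gap there is not peculiar to pain.

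The count of stated by-arm pain results during treatment is 0.

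**2. What can Visit 20 recover?** Inputs are the windows in section 6.1.1 and the longest recall period in section 6.2, 7 days.
- Visit 19 to Visit 20: 7 ± 3 = 4 to 10 days.
- Visit 18 to Visit 19: 6 to 10 days.
- Visit 18 to Visit 20: at least 6 + 4 = 10 days, which exceeds 7.

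The 7-day rating at Visit 20 therefore reaches Visit 19 at most, which is 1 of 18 sessions, and none if Visit 20 falls 8-10 days after Visit 19. Section 9.5.1 does not say which pain rating is the co-primary one. If it is the 24-hour or current rating, the reach is 0.

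**3. What do the ratings already scheduled cover?** Take the weekly 7-day ratings after the first session (Visits 5, 8, 11, 13, 15, 17, 18, 19) and count sessions in the 7 days before each.
- Shortest gaps (2 days to Visit 16, then 6): Visits 2-14, 16, 17 and 18, so 16 of 18 sessions.
- Longest standard gaps (3 days to Visit 10, 6 to Visit 16, then 10): Visits 3, 4, 6, 7, 10, 12 and 14, so 7 of 18.

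The second figure is not a floor, because section 6.1.2 allows a 30-day extension that could lower it. At full attendance the schedule yields 230 × 8 = 1,840 weekly ratings after the first session and 230 × 18 = 4,140 current-pain ratings. None enters a stated by-arm pain result.

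**4. How should worsening be counted?** One obvious measure is the worst change from Visit 1 over the eight weekly ratings, with +3 points as the cut-off. It was simulated with no treatment effect, taking r = 0.7 from section 9.2. Assumptions: mean NRS 4 to 6, equal correlation between all ratings, whole-number scores limited to 0-10, and a Visit 1 score of at least 3.

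| SD | Participants at +3 or more on the worst of 8 |
|---|---|
| 75% of mean (section 9.2) | about 33-38% |
| 40% of mean (assumed) | about 8-27% |

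The 95% half-width for a difference between arms, at an assumed 115 per arm, is 1.96 × √(2p(1−p)/115). At p = 0.35 this is 1.96 × √(0.455/115) = 0.123, or about 12 points. A baseline of 8 would need a score of 11 to rise by 3, so baselines of 8-10 cannot meet the cut-off.

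**The case against.** **Participants are protected.** Each game session opens with a health screen, sudden-onset muscle or joint pain stops the session, a second episode leads to withdrawal, and committees review safety (sections 6.2, 6.2.6, 7.1, 7.6 and 12). This stands: the point is not about protection. None of these provisions promises a count by arm.

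**The table may exist elsewhere, or be added later.** Adverse event handling is referred to Appendix A, and section 7.6 cites a Data and Safety Monitoring Plan. Neither is supplied, so the point covers only the supplied text. Section 9 does not forbid the table either. Fixing the summary and cut-off in advance is what guards against selective reporting.

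**The risk statement is about reaching.** True: it comes from the paragraph on the reaching task, which both arms perform, and which goes on to report no sustained aggravation in over a decade. But section 7 likens game movements to reaching, and its game-play text also speaks of reducing the risk of exacerbating symptoms.

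**Stronger readings that the documents do not support.**
- A reader might infer that every flare over before Visit 20 is lost. The 7-day rating, if it is the one analysed, can still register a flare that settled within that window.
- A reader might see a contradiction between the back-pain exclusion and the serious-event wording "may worsen a pre-existing condition". Serious events are a class of adverse events, so the exclusion in the same section most naturally governs.
- Section 6.2.4 heads its list "Treatment visit assessments for each visit 2-19 include the following" and includes the 7-day rating, which might suggest collection at every visit. The same list holds the reaching paradigm, which sections 6.2 and 9.5.2 place weekly for expectancy (9.5.2 for flexion too). The weekly schedule is the better reading.

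**Conclusion.** The point holds, limited to flares during treatment that settle before the Visit 20 recall window. In the supplied text such a flare is outside adverse event recording and outside every stated by-arm pain result, and Visit 20 reaches at most 1 of 18 sessions. A flare can act indirectly, through withdrawal or exclusion from the per-protocol set, but neither is a stated by-arm pain result.

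The documents do not support reading this as a flaw in the primary analysis or as evidence that harm is being concealed: the ratings are collected, and a flare lasting into the window could still be seen. The visit-window arithmetic rests on the protocol alone. The 8-38% range and the 12-point half-width rest on the assumptions stated above, since the plan gives no flare rate. Confidence is medium because two safety documents are unseen. The change is worth making but optional.

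**What to change.** Add to section 9.6 one descriptive by-arm safety summary, with 95% confidence intervals and no tests, among participants who started at least one session:

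- (a) Mean and distribution of change in 7-day NRS from Visit 1 at each weekly treatment visit. Include the proportion worsened by a cut-off that the sponsor fixes in advance, counted at each visit or on at least two consecutive weekly ratings rather than on the single worst rating. Give the number of ratings available per arm.
- (b) Current-pain NRS by treatment visit.
- (c) Counts of sessions stopped and participants withdrawn for sudden-onset pain under section 6.2.6.

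The cost is SAP wording and one set of tables from data already scheduled, with no new visits and no change to the sample size.

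The limits should be stated with the table. Any cut-off partly counts ordinary fluctuation, the count depends on how many ratings a participant gives, and high baselines cannot meet a +3 rule. Intervals may be about 12 points either side. Only the contrast between arms can be interpreted, and a null contrast would not show that flares are absent.

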1.2 Secondary Objectives

Secondary objectives are to examine potential mechanisms of pre- to post-treatment changes in clinical outcomes and maintenance of treatment gains. Participants in the experimental group will exhibit greater pre- to post-treatment decreases in pain/harm expectancy and increases in lumbar flexion as compared to the control group (Hypothesis 2.1). Decreases in pain/harm expectancy and increases in lumbar flexion will be positively related to pre- to post-treatment reductions in pain and disability (Hypothesis 2.2). Examination of maintenance of treatment gains will occur at 1-, 6-, 12-, 24-, and 48-weeks post-treatment. Relative to the control group, participants in the experimental group will continue to show lower levels of pain and disability at each time point as well as increased activity in their natural environment (Hypothesis 3).

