This project is a Phase II RCT in which CLBP participants will be randomly assigned to one of two intervention arms. Those assigned to the experimental group will play immersive games that will encourage progressively larger lumbar flexion excursions at each game level and across treatment sessions. Those in the control group will play the same immersive games, but the parameters of the game will require smaller excursions of lumbar flexion to successfully complete gameplay. Treatment frequency and duration is based on existing evidence that graded activity and graded exposure interventions, typically lasting 6-12 weeks with 8-18 treatments sessions, result in significant reductions in disability.^{44,43} Accordingly, participants in this study will complete 18 visits over 9 weeks with the number of sessions tapered across weeks (i.e., 3 sessions/week in weeks 1-3, 2 sessions/week in weeks 4-6, and 1 session/week in weeks 7-9). Our co-primary outcome variables will be change in pain and change in disability from baseline to 1-week post-treatment (Aim 1). We will also examine changes in expectations of pain/harm and lumbar flexion as potential mechanisms of change in pain and disability (Aim 2). Aim 3 will examine maintenance of treatment gains at 1-, 6-, 12-, 24-, and 48-weeks post-treatment.

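### The Hypothesis 2.2 model states no change term and no within-person/between-person split, so on its natural reading it can report linked changes that do not exist

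*Combined protocol and SAP*

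**What the plan says.** Section 1.2 states Hypothesis 2.2 as a relation between changes: "Decreases in pain/harm expectancy and increases in lumbar flexion will be positively related to pre- to post-treatment reductions in pain and disability". Sections 9 and 9.6 repeat it.

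Section 9.6 gives one model for it: "For hypothesis 2.2, pain/harm expectancy and lumbar flexion will serve as the outcome variables". Linear and quadratic time, treatment group and their interactions are on the predictor side, and "pain, and disability will be predictor variables". The models in that section take "time (pre-treatment, 1, 6, 12, 24, and 48 weeks) as a within-subject fixed effect". No change score, person mean, centred term or pain-by-time term is stated, and no coefficient or combination is named as the test. For multiplicity, "Holms procedure will be used to control familywise type-I error rate for post-tests at .05".

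The plan describes pain and disability in two ways. Section 9 says "Our co-primary outcome variables will be change in pain and change in disability from baseline to 1-week post-treatment". Section 9.5.1 lists them as measures taken at visit 1 and visits 20-24.

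Section 9.2 says that the calculation leading to 209 participants covers Hypotheses 2.1, 2.2 and 3.

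**The concern.** Beside linear and quadratic time over six visits, the natural reading is that pain and disability enter as their values at each visit. A random intercept does not then remove between-person association from the coefficient of a time-varying predictor. The coefficient is a weighted average of two slopes: how a person's mechanism score moves when that person's pain moves, and how people with more pain differ from people with less. Hypothesis 2.2 concerns only the first. If people in more pain simply expect more pain, the coefficient can be significant although no changes are linked.

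Which variable is placed on the outcome side is not the problem, because a positive relation is symmetric.

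At stake is the mechanism claim of Aim 2. The trial could report that expectancy or flexion changed along with pain and disability when those changes were unrelated. Hypotheses 1, 2.1 and 3 have their own tests and are not affected.

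**Working it through.** **1. What the 209 is.** Inputs from section 9.2: standardized effect 0.45, slope variance 0.30, residual variance 1, power 0.80, alpha 0.05 (two-sided assumed). For a group difference in linear slopes over five equally spaced occasions, the sum of squared centred times is 10. The slope difference is g = 0.45 × √0.30, so g² = 0.2025 × 0.30 = 0.06075. By the normal approximation,

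N = 4 × (1.960 + 0.842)² × (0.30 + 1/10) / 0.06075 = 206.7,

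and the noncentral F gives 209. The plan's figure is thus reproduced as power for a treatment-by-time difference. No correlation between changes enters it.

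**2. Why the levels model is biased, by hand.** Take N = 230 × 0.9 = 207 and a stable share of 0.7 for every measure. The 0.7 is the plan's Aim 1 pre-post correlation, extended here by assumption to the mechanisms and to 48 weeks. Assume a pain-disability correlation of 0.5, a between-person correlation r of the mechanism with each, and no within-person link.

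- Six visits. Within-person information per participant is (6 − 1) × 0.3/0.3 = 5. Between-person information is 6 × (0.7 + 0.3/6) / (6 × 0.7 + 0.3) = 4.5/4.5 = 1. The between-person slope therefore has weight 1/6.
- That slope, per predictor, is 0.7r / (0.75 × 1.5). At r = 0.3 it is 0.187, so the spurious coefficient is 0.187/6 = 0.031 SD per SD.
- The noncentrality of the two-coefficient test is 207 × 6 × 3 × 0.0311² = 3.6, which rejects in about 38% of trials. At r = 0.5 the same steps give 0.052, 10.0 and about 82%.
- With baseline and 1 week only, the weight is 1/2 and the rates are about 74% and 99%.

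**3. Simulation.** Model as written without covariates, random-intercept REML, N = 207, 2,000 trials per cell, no linked change. Ranges are over pain-disability correlations of 0.3, 0.5 and 0.7.

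| False-positive rate | r = 0 | r = 0.3 | r = 0.5 |
|---|---|---|---|
| Six visits, two-coefficient test | 5-6% | 36-45% | 80-92% |
| Six visits, either coefficient | 9-10% | 21-44% | 46-89% |
| Six visits, both required | not tabulated | 1-3% | 1-34% |
| Baseline and 1 week, two-coefficient test | 5-6% | 69-83% | over 99% |

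A single change-on-change test rejects in 4-6% of trials. With a pain-disability correlation of 0.5, smaller correlations also matter: a separate run of 1,000 trials per cell gave 9% and 19% with six visits at r = 0.1 and 0.2 (two-coefficient test).

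**4. Sensitivity (six visits, pain-disability correlation 0.5).**

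- Stable share 0.5 or 0.8: 35% or 41% at r = 0.3, and 78% or 89% at r = 0.5 (two-coefficient test).
- The plan notes that "LME models permit numerous alternative error covariance structures". Modelling residual autocorrelation of 0.5 still leaves 35% and 79% at r = 0.3 and 0.5 (400 trials).
- Adding a random slope leaves 23% and 48% for the pain coefficient alone (N = 209, about 185 trials each).
- Splitting pain and disability into person mean and within-person deviation brings each coefficient to 4-6%.

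**The case against.** **The plan may mean changes.** Sections 1.1 and 9 call the co-primary outcomes changes. If section 9.6 inherits that meaning, the false positives disappear. Section 9.6 does not say so, however, and section 9.5.1 lists values at each visit. Either way the plan needs a sentence that settles it.

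**The size depends on assumptions.** No document gives a between-person correlation, and at zero the two-coefficient test holds its level. One value is applied to all three mechanisms, although sections 2.2.2 and 2.2.4 link lumbar flexion to pain-related fear rather than to pain level. The rate also depends on a decision rule that the plan does not state: requiring both coefficients gives only 1-3% at r = 0.3. This stands, and the percentages are conditional illustrations. But the plan does not adopt the strict rule, and at r = 0.5 that rule reaches 34% when the pain-disability correlation is 0.3.

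**The spurious coefficients are small.** Over six visits they are about 0.02-0.04 SD per SD at r = 0.3 and 0.05-0.07 at r = 0.5. This also stands: an analyst who looked at size as well as significance would be less misled. With two visits they are larger, at 0.07-0.10 and 0.12-0.19.

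**The hypothesis is secondary and associational.** That limits the severity. It does not make a coefficient that blends two associations a valid test of linked change.

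**Conclusion.** The concern holds and should be fixed. Two parts rest on the text alone: the plan does not say whether pain and disability enter as levels or changes or which coefficient decides Hypothesis 2.2, and it gives no basis for the power of that hypothesis.

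The false-positive rate depends on the levels reading, on a non-zero between-person correlation and on the decision rule. For the two-coefficient test over six visits it is 36-45% at an assumed correlation of 0.3 and 80-92% at 0.5, with a stable share of 0.7 and 207 participants. The primary analysis is not touched.

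**What to change.** **Preferred.** Fit six models. For pain and for the RMDQ, regress the baseline-to-1-week change on treatment and on the baseline-to-1-week change in one mechanism at a time: expected pain, expected harm, lumbar flexion. Apply Holm's procedure across the six tests and state that they decide Hypothesis 2.2. The SAP should also name the pain rating (section 6.2 has three), the summary of expectancy and flexion over targets (and hands, for flexion), and the handling of a missing week 1 value in line with section 9.3.

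**If the all-visit mixed model is kept.** Use one time-varying predictor per model, split it into person mean and within-person deviation, enter visit as categories by treatment, model residual autocorrelation, and test the within-person term. This answers a wider question, out to 48 weeks. Its error is 4-6% with categorical visits. With quadratic time and a one-step drop after baseline it is about 7% for drops of 0.13 and 0.40 SD (control and experimental), and 8.5-10.1% for 0.3 and 0.6 SD. Autocorrelation of 0.5 left unmodelled gives 8-9%.

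In either case, state the within-person correlation assumed for Hypothesis 2.2, or stop attributing 80% power to it at 209. Neither option needs weekly lumbar flexion, which sections 5.1, 6.2 and 9.5.2 describe inconsistently.

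**Cost.** SAP wording and modest analysis work before unblinding, with no new data or visits. The price is power. For change-on-change with one covariate, power is approximately Φ(atanh(ρ) × √(207 − 4) − 1.960):

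- ρ = 0.1: Φ(0.1003 × 14.25 − 1.960) = 30%.
- ρ = 0.2: Φ(0.2027 × 14.25 − 1.960) = 82%.
- 80% power needs ρ = 0.19 unadjusted, or 0.24 at the first Holm step (0.05/6).
- Under Holm with all six links real, per-test power is about 13% at 0.1 and 72% at 0.2. This assumes change correlations of 0.6 between expected pain and harm, 0.2 between flexion and each, and 0.5 between pain and disability.

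The all-visit within-person term has 90% power at 0.1 (75% at 0.05/6), but only if the link is the same at all visits, errors are independent and all 207 attend every visit.
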